11.5.4. AE (Event) Density and Incidence Rate

AE density, also referred to as event density, will be calculated as the number of events in a given period divided by the total person time on treatment (in years) of subjects at risk at the beginning of the same period. The incidence rate for an AE will be calculated as the number of subjects experiencing that AE within a given period divided by the total person time on treatment (in years) of subjects at risk at the beginning of the same period.

To enhance the data presentation and to aid comparison between treatment groupings, all AE densities and all incidence rates of AEs will be presented per 100 person-years (by multiplying the above defined statistics by 100).

11.6. Appendix 6: Premature Withdrawals & Handling of Missing Data

11.6.1. Premature Withdrawal

The reasons for subjects not completing the treatment period will be recorded in the eCRF. Subjects who discontinue active participation in the study will no longer receive the randomized study treatment. Immediately upon discontinuation from active participation in this study, these subjects should complete the early withdrawal assessments and return 8 weeks later for the follow-up assessments.

The reasons for subjects not completing the study will be also recorded in the eCRF. Subjects who are withdrawn will not be replaced.

11.6.2. Missing Date Imputation

In general, partial dates will be imputed as follows:

A partial event start date, partial start dates of prior and concomitant medications or partial diagnosis date will be assumed to be the earliest possible date consistent with the partial date.

- If year is missing, the year will be assumed to be the year part of informed consent date of that subject;
- If month is missing, the month will be assumed to be January;
- If day is missing, it will be assumed to be the first day of the month.
- In the case of a completely missing start date, the start date will be assumed to be prior to date of the first administration of study drug.

Partial event or medication stop dates will be assumed to be the latest possible date consistent with the partial date.

- If month is missing, it will be assumed to be December;
- If day is missing, it will be assumed to be the last day of the month.
- In the case of completely missing stop date, the stop date will be assumed to be after the date of the last study visit; the event or medication are considered as ongoing.

For AE date imputation this rule will be followed but will be more conservative in nature consistent with the therapy phase (see [Appendix 4: Treatment Periods](#) for details).

Since only the year of birth is recorded for subjects in this study, the age of the subjects for analysis purposes is calculated using June 30 of the birth year as the imputed subject birth date.

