7.4.1.1. Time period and Frequency for collecting AE and SAE information

AEs and SAEs will be collected from the start of Study Treatment until the follow-up contact (see Section 7.4.1.3), at the timepoints specified in the Time and Events Table (Section 7.1).

Medical occurrences that begin prior to the start of study treatment but after obtaining informed consent may be recorded on the Medical History/Current Medical Conditions section of the eCRF.

Any SAEs assessed as related to study participation (e.g., protocol-mandated procedures, invasive tests, or change in existing therapy) or related to a GSK product will be recorded from the time a subject consents to participate in the study up to and including any follow-up contact.

All SAEs will be recorded and reported to GSK within 24 hours, as indicated in [Appendix 5](#).

Investigators are not obligated to actively seek AEs or SAEs in former study subjects. However, if the investigator learns of any SAE, including a death, at any time after a subject has been discharged from the study, and he/she considers the event reasonably related to the study treatment or study participation, the investigator must promptly notify GSK.

NOTE: The method of recording, evaluating and assessing causality of AEs and SAEs plus procedures for completing and transmitting SAE reports to GSK are provided in [Appendix 5](#)

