11.4. Appendix 4: Treatment Periods

For classifying AEs (including hypoglycemic events), the therapy periods will be defined as:

- **Pre-therapy:** The onset date of the AE is before the start date of randomized study medication. If the onset date of the AE is on the start date of randomized study medication, the AE will be considered as on-therapy.
- **On-therapy:** The onset date of the AE is on or after the start date of randomized study medication and within 25 days after the date of last dose.
- **Post-therapy:** The onset date of the AE is more than 25 days after the last date of randomized study medication.

For immunogenicity data and other safety parameters that are assessed prior to administration of randomized study medication on dosing days, the therapy periods will be defined as:

- **Pre-therapy:** The assessment date is on or before the start date of randomized study medication.
- **On-therapy:** The assessment date is after the start date of randomized study medication and within 25 days after the date of last dose.
- **Post-therapy:** The assessment date is more than 25 days after the last date of randomized study medication.

For an AE with an incomplete start date where the year and month are present while the day is missing, or where the year is present while both month and day are missing, the date is imputed in a dynamic way consistent with the partial date information so that the resulting AE therapy period assignment based on the imputed date is the most conservative possible, where the order from the most to the least conservative is: on-therapy phase > post-therapy phase > pre-therapy. Note that if the AE stop date is present, then the imputed start date will always be on or prior to the stop date.

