3.61.	Safety		Overview of On-therapy Adverse Events of Special Interest		

CONFIDENTIAL

200952

Safety : Tables					
No.	Population	IDSL / TST ID / Example Shell	Title	Programming Notes	Deliverable [Priority]
3.71.	Safety		On-therapy Hypoglycemic Events by SAE Status, Relationship to Study Medication, and Withdrawal Status		
3.72.	Safety		On-therapy Hypoglycemic Events by Treatment, Symptom, Severity, Intervention and Action Taken		
3.73.	Safety		On-therapy Hypoglycemic Events by Blood Glucose Level		
3.80.	Safety		On-therapy Hypoglycemic Events over Time by Onset Week		
3.91.	Safety		On-therapy and Post-therapy Cardiovascular Adverse Events		
3.101.	Safety		On-therapy and Post-therapy Thyroid Adverse Events Reported by the Investigator		
3.102.	Safety		On-therapy and Post-therapy Thyroid Adverse Events Identified by a Customized MedDRA Query		
3.111.	Safety		Summary of Gastrointestinal Adverse Events		
3.112.	Safety		On-therapy Gastrointestinal Adverse Events		
3.113.	Safety		On-therapy Serious Gastrointestinal Adverse Events		
3.114.	Safety		On-therapy Treatment-related Gastrointestinal Adverse Events		
3.115.	Safety		On-therapy Gastrointestinal Adverse Events Leading to Permanent Discontinuation of Study Treatment before Scheduled End of Treatment Period		
3.116.	Safety		On-therapy Gastrointestinal Adverse Events over Time		
3.117.	Safety		On-therapy Gastrointestinal Adverse Events by Onset Week		
3.118.	Safety		Kaplan-Meier Analysis of Time to First Occurrence of a Gastrointestinal Adverse Event		
3.119.	Safety		On-therapy Nausea over Time		
3.120.	Safety		On-therapy Diarrhea over Time		

Safety : Tables					
No.	Population	IDSL / TST ID / Example Shell	Title	Programming Notes	Deliverable [Priority]
3.121.	Safety		On-therapy Vomiting over Time		
3.122.	Safety		On-therapy Nausea or Vomiting over Time		
3.131.	Safety		On-therapy and Post-therapy System Allergic Reactions Identified by the Investigator		
3.132.	Safety		On-therapy and Post-therapy System Allergic Reactions Identified by a Customized MedDRA Query		
3.133.	Safety		Kaplan-Meier Analysis of Time to First Occurrence of a Systemic Allergic Reaction Reported by the Investigator		
3.134.	Safety		Kaplan-Meier Analysis of Time to First Occurrence of a Systemic Allergic Reaction Identified by a Customized MedDRA Query		
3.141.	Safety		On-therapy and Post-therapy Injection Site Reactions		
3.142.	Safety		Kaplan-Meier Analysis of Time to First Occurrence of an Injection Site Reaction		

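### The conservative date rule for adverse events covers only start dates with a known year, so a wholly undated event, even an injection site reaction, defaults to pre-therapy

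*SAP*

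**What the plan says.** SAP 11.6.2 covers events, medications and diagnoses together. Two of its conventions matter here. For an absent year: "If year is missing, the year will be assumed to be the year part of informed consent date of that subject". For an absent date: "In the case of a completely missing start date, the start date will be assumed to be prior to date of the first administration".

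The section then singles out AEs: "For AE date imputation this rule will be followed but will be more conservative in nature consistent with the therapy phase", with a reference to Appendix 4 (SAP 11.4). Appendix 4 chooses the imputed date that gives the most conservative therapy phase, and states that "the order from the most to the least conservative is: on-therapy phase > post-therapy phase > pre-therapy". It limits this to AE start dates "where the year and month are present while the day is missing, or where the year is present while both month and day are missing". It also keeps the imputed start on or before any recorded stop date.

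Appendix 4 defines a pre-therapy AE thus: "The onset date of the AE is before the start date of randomized study medication". An onset on the day of first dose counts as on-therapy.

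**The concern.** The two sections do not meet. The convention that gives the least favourable safety count is confined to dates with a known year. The cases with the least information fall back on a rule that moves the event out of the treatment period.

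That is an implausible default for this trial. Protocol 7.4.1.1 says that "AEs and SAEs will be collected from the start of Study Treatment until the follow-up contact", so an undated non-serious event on the AE page most likely began after first dose. A reaction at a study injection site must have. The default is also out of line with the SAP's treatment of another missing AE attribute: under 8.2.4.3, a missing or unknown relationship after treatment start is counted as treatment-related.

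Injection site reactions are part of a named secondary objective, and the protocol's risk table says the liquid product's lower pH and larger volume at 50 mg may change their profile. A rule that can only lower the count should not apply to them by default.

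**Working it through.** The documents give no figure for undated AEs, so there is no plan figure to reproduce. The check is to trace each kind of incomplete AE start date through the two sections.

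| Missing part of AE start | Named in Appendix 4? | Explicit rule | Resulting phase |
|---|---|---|---|
| Day | Yes | On-therapy-first | Most conservative phase the known parts allow |
| Day and month | Yes | On-therapy-first | Most conservative phase the known parts allow |
| Year (month known) | No | Consent year (11.6.2) | Pre-therapy whenever that date falls before first dose |
| Whole date | No | Before first dose (11.6.2) | Always pre-therapy |

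**Missing year.** Suppose a subject consents and starts treatment in November and has a reaction the next February, recorded without a year. February lies inside the 26-week treatment period. The rule dates the event to February of the consent year, about nine months before consent. If consent falls in late December and first dose in January, which the two-week screening window allows, every missing-year onset is placed before first dose, whatever its month.

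**Effect on the displays.**
- Treatment-emergent AEs are on-therapy plus post-therapy events (SAP 8.2.4.2), so a pre-therapy event is not counted.
- Table 3.141 is titled "On-therapy and Post-therapy Injection Site Reactions". Tables 3.143 and 3.144 are on-therapy only. All three omit it.
- Time to first injection site reaction follows the gastrointestinal method (SAP 8.2.2 and 8.2.7.5). That method uses the first on-therapy onset and censors event-free subjects at last dose plus 25 days. A subject whose only reaction is undated would most naturally be censored as event-free.
- The event stays in the injection site reaction listing (Listing 25) and the AE listing (Listing 136), and would fall into the pre-therapy AE table (Table 3.13).

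**Scale.** The inputs are about 150 randomized subjects per arm (Protocol 9.2.1), taken as the safety denominator, and an assumed number of subjects whose only reaction is undated.
- One subject: 1/150 = 0.0067, or 0.67 percentage points.
- Three subjects: 3/150 = 0.020, or 2.0 percentage points.

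The range of one to three is an assumption. A subject who also has a dated on-therapy reaction changes the proportion by nothing.

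**The case against.** The best defence is that SAP 11.6.2 states its intent: AE dates are to be treated more conservatively, by therapy phase, and Appendix 4 ranks pre-therapy last. On that view the wholly missing case is an ambiguity that a careful programmer would resolve correctly. The intent is clear. However, the same sentence says the general rule will be followed, and Appendix 4 gives no instruction for a missing year or a missing date. The only explicit text points the other way.

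The defence is right that such events should be rare and visible. Site staff give the injections at weekly visits, AEs are reviewed at each visit, injection site reactions have their own eCRF page, and the database is cleaned before release. A pre-therapy injection site reaction would stand out in a listing. The rule is the same in both arms of a double-blind trial and safety is descriptive, so no between-arm bias is shown.

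A reader might infer three stronger things that the documents do not support:
- **That the SAP contradicts Protocol 7.4.1.1.** It does not. The same section records related SAEs from consent, the schedule marks AE review at screening, and the SAP plans pre-therapy AE tables. A pre-therapy class is legitimate; it is only an implausible default for an undated non-serious event.
- **That an undated rescue drug would leave post-rescue HbA1c in the pre-rescue analysis.** Neither document says that the rescue date is derived from imputed medication start dates. The primary analysis keeps post-rescue values in any case.
- **That these events vanish from the report.** They leave the phase-restricted tables and remain in the listings.

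**Conclusion.** The point holds as a gap in the AE date rule. As written, an AE with a completely missing start date is classed as pre-therapy, and one with a missing year can be. This defeats the SAP's stated conservative intent on a named safety endpoint. AEs with the year present are properly protected.

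The practical effect is probably very small, though the documents give no count. The figure of about 0.67 percentage points per affected subject rests on about 150 safety subjects per arm and on that subject having no other dated reaction. The direction is certain: in the on-therapy and treatment-emergent tables, the rule can only undercount. It is worth correcting because the rule is stated, gives an implausible result for this class of event, and is easy to change. The primary HbA1c analysis is not affected.

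**What to change.** Extend Appendix 4 to AE start dates with a missing year or no date at all, using the same on-therapy-first order:
- **Year missing:** choose the year that gives the most conservative phase compatible with the known parts and any stop date.
- **Date completely missing:** impute the date of first dose, unless a recorded stop date precedes first dose. Appendix 4 counts that day as on-therapy. An actual date is needed because assigning a phase alone would leave the time-to-first-event analyses without an onset. This gives the earliest on-therapy onset, so report by arm how many onsets were imputed this way.

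In 11.6.2, state that the general conventions for a missing year and a missing start date do not apply to AEs, and cross-refer to Appendix 4.

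The cost is two or three sentences in the SAP and a small change to the date-imputation program. No new data are needed.

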11.6.3. Handling of Missing Data

11.6.3.1. Impact of Missing Data on Primary Endpoint

Missing data, in the context of the primary analysis at Week 26, refer to those cases where the Week 26 HbA1c value is not available or was not collected or subject is lost to follow-up or withdraws consent. Missing data will be imputed in the primary MMRM analysis. To avoid bias in non-inferiority trials due to missing data, special attention will be paid to the handling of missing data in statistical analysis. Although, it is expected that the pattern of missing data will be similar in both treatment arms given that the treatment arms are the same drug but different formulations and it is expected that the impact of missing data on the primary endpoint to be minimal. Imputation under the non-inferiority null hypothesis [Koch, 2008] for all missing data for the primary analysis at Week 26 will be implemented.

11.6.3.2. Extent of Missing Primary Analysis Data

Missing data is expected to arise mainly from subjects missing complete visits. The amount of missing data for those baseline covariates included in the statistical analysis is expected to be none or at worst minimal. If it should occur, that subject will effectively be lost to analysis. Missing data for HbA1c between two non-missing visits will be considered missing at random (intermediate missing data).

In this study, subjects who withdraw from treatment will stay in the study. In the eCRF, the reason for treatment discontinuation and the reason for withdrawal from the study are collected separately. Whenever the HbA1c value at Week 26 is missing (end of the study), the reason can be determined based on available data in these two locations. The reason for missing data can be classified as lost to follow-up or withdrawal of consent or investigator discretion.

11.6.3.3. Reasons for Withdrawal

Reasons for withdrawal from the study are lost to follow-up or withdrawal consent or investigator discretion. All subjects who discontinuation from investigational product due to the reason listed under protocol Section 5.5 will remain in the study and efficacy and safety data will be collected.

11.6.3.4. Sensitivity Analysis Under Missing Not At Random (MNAR)

The impact of missing data will be explored, as outlined below, for the ITT Analysis Population only.

Examination of Missing Data Patterns

It is expected that the pattern of missing data will be similar in both treatment groups given the each treatment group is using the same drug but different formula.

To examine the nature of missing data, cohorts of subjects will be defined based on the scheduled assessments (HbA_{1c} change from baseline) that were completed at Weeks 1, 4, 8, 12, 16, 20, and 26.

- Subjects who have week 1 assessment only
- Subjects who have assessments up to and including Week 4 only
- Subjects who have assessments up to and including Week 8 only
- Subjects who have assessments up to and including Week 12 only
- Subjects who have assessments up to and including Week 16 only
- Subjects who have assessments up to and including Week 20 only
- Subjects who have assessments up to and including Week 26.

The number and percentage of subjects on each treatment in the 7 cohorts defined here will be tabulated. Graphical methods will be used to examine changes from baseline over time to assess the pattern of outcomes prior to withdrawal.

Sensitivity Analyses

The sensitivity of the results of analysis to the method of handling missing values will be investigated, especially if the number of missing values is substantial or if the characteristics of missing values differ between treatment groups.

To assess the impact of subjects who discontinued investigational product and stayed in the study; exclusion of data after treatment discontinuation may also be performed if a significant number of subjects discontinue study medication prior to Week 26. On treatment data will be analyzed using the same imputation/MMRM model as described in Section 7.1.1.1. The imputation will be performed for missing value at Week 26 due to any reason and also available value at Week 26, but off-treatment.

Sensitivity analyses using a different type of multiple imputation method will be conducted. Firstly, missing data between two non-missing time points (i.e. intermittent missing data) will be considered missing at random (MAR). Secondly, missing data after the last available assessment due to any reasons (i.e. monotone missing data) will be imputed using last mean carried forward (LMCF), that is Missing Not At Random (MNAR) (Carpenter and Kenward, 2013). Thirdly, this approach assumes that a constant rate of increase in HbA_{1c} change from Baseline is experienced by subjects following withdrawal from the study. The imputed values based on LMCF will be then updated with an added delta using the following rates of HbA_{1c} increase: 0%/month, 0.1%/month, and 0.2%/month to explore the potential impact as in a tipping-point analysis. For each treatment group, these 3 rates will be assumed, resulting in 9 scenarios. The resulting treatment differences and associated P-values for non-inferiority will be tabulated against the varying rates of HbA_{1c} increase. This estimand is one where those who withdraw are assumed to revert to an unstable treatment regimen with an increasing rate of HbA_{1c}. For each imputation data set, an analysis of variance (ANCOVA) will be carried using Week 26 data, both actual and imputed, using the same covariates as in the primary analysis. Contrasts of interest will be estimated and then combined across

imputations using standard multiple imputation rules. The details of implementing this multiple imputation approach using delta method in combination with LMCF are the following:

- Step 1: Multiple Imputation under MAR ($K=100$ times)
 - Run PROC MI for all subjects BY treatment group (specifying the options chain=multiple in the MCMC statement).
 - As a result 100 sets of mean vectors (μ) and variance-covariance matrices (Σ) for each treatment group are simulated from the posterior distribution.
 - Each of the above 100 simulated parameter sets leads to a separate imputed dataset, in which the missing values (Y_2) for each subject are replaced by values drawn randomly from their conditional distribution given the observed values (Y_1). This condition distribution (Y_2/Y_1) is multinomial with mean $\mu_2 + \Sigma_{21} \Sigma_{11}^{-1} (Y_1 - \mu_1)$ and variance-covariance matrix $\Sigma_{22} - \Sigma_{21} \Sigma_{11}^{-1} \Sigma_{12}$. So, 100 imputed datasets are generated.
- Step 2: Multiple Imputation using LMCF ($K=100$ times)
 - For each imputed dataset from Step 1, update the imputed values (post-last observation) as follows:
 - For each subject per treatment group, if there are any imputed values after the last observation (Y_p, imp), first split the simulated mean vector (μ) into three parts: μ_b (prior to last obs), μ_{last} (last obs) and μ_p (post last obs) and then update these imputed values as $Y^*_{p, \text{imp}} = (Y_p, \text{imp} - \mu_p + \mu_{\text{last}})$. Repeat for all subjects and for both treatment groups.
 - Repeat for the 100 imputed datasets from Step 1.
- Step 3: Multiple Imputation using Delta method ($K=100$ times)
 - Calculate delta value for each subject at each visit post-last observation
 - Let γ_1 and γ_2 be the rates of HbA1c increase per month after the last observation for the liquid and lyophilized treatment group, respectively.
 - Let τ be the length of time between visits. Also, consider 1 month=4 weeks and determine τ using the visit week values. For example, time between visits Week 16 and Week 20 is 4 weeks (i.e. 1 month) and time between visits Week 16 and Week 26 is 10 weeks (i.e. 10/4=2.5 months).
 - For each subject and each visit post-last observation, a delta value will be derived according to the treatment group the subject was randomized to and time between the last observation visit and the present visit (τ). If the subject belongs to the liquid treatment group, the delta value = $\gamma_1 \times \tau/4$; if the subject belongs to the lyophilized treatment group, the delta value = $\gamma_2 \times \tau/4$.
 - For each updated imputed dataset from Step 2 increase the imputed values post-last observation by the corresponding delta values (per subject per visit post-last observation).
 - Repeat for the 100 imputed datasets from Step 2

- Step 4: Repeat Step 1, Step 2 and Step 3 for 9 scenarios based on 3 different rates of HbA1c increase for each treatment group (i.e. $\gamma_1, \gamma_2=0/\text{month}$, $0.1/\text{month}$ and $0.2/\text{month}$)
- Step 5: For each scenario, apply ANCOVA analysis at Week 26 for each of the 100 imputed dataset and save the difference in LSmeans between treatment group and the associated standard error from each of the 100 analyses.
- Step 6: For each scenario, combine the 100 set of analysis results using Rubin's rules ([Rubin, 1987](#)) via SAS PROC MIANALYZE. The treatment differences, confidence intervals and p-values will be estimated by MODELEFFECTS and STDERR statement. Use the degrees of freedom (EDF) you would have if the dataset were complete.

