11.11. Appendix 11: Model Checking and Diagnostics for Statistical Analyses

11.11.1. Model Checking and Diagnostics for Statistical Analyses

1. Example SAS code for the primary efficacy analysis with imputation

Step 1a: Transpose the data horizontally and then impute data assuming missing at random (EFFIM)

```
PROC MI DATA= EFF OUT= EFFIM NIMPUTE=100 SEED=4408572;
  BY TRT01PN;
  MCMC CHAIN=multiple;
  VAR BASE CHG_W1 CHG_W4 CHG_W8 CHG_W12 CHG_W16 CHG_W20 CHG_W26;
  RUN;
```

Note: need to remove all imputed values before Week 26 and retain imputed values at Week 26 only.

Step 1b: Add 0.4 to the imputed value at Week 26 in the liquid product arm and transpose data in vertical structure (EFFIM2)

Step 2: Exclude HbA1c change from baseline at Week 1 and perform MMRM for each imputed dataset

```
Ods output SLICES=SLICE LSM SLICEDIFFS=SLICEDIFF;
```

```
PROC MIXED DATA= EFFIM ;
  BY _imputation_;
  CLASS USUBJID REGION WGTGR1 AGEGR1 PRIORDTX TRT01PN AVISITN;
  MODEL CHG= BASE REGION WGTGR1 AGEGR1 PRIORDTX TRT01PN AVISITN
  TRT01PN*AVISITN BASE*AVISITN/ DDFM=KR;
  REPEATED AVISITN/SUB=USUBJID TYPE=UN;
  SLICE TRT01PN*AVISITN/sliceby(AVISITN='26') means pdiff cl cov;
  RUN;
```

Step 3: Combine results using PROC MIANALYZE

```
PROC SORT DATA=SLICE LSM; BY TRT01PN IMPUTATION; RUN;
PROC MIANALYZE DATA=SLICE LSM EDF=CDF*;
BY TRT01PN;
MODELEFFECTS ESTIMATE;
STDERR STDERR;
RUN;
```

```
PROC MIANALYZE DATA=SLICEDIFF;
MODELEFFECTS ESTIMATE;
STDERR STDERR;
RUN;
```

*CDF=complete-data degrees of freedom. This is used to calculate the adjusted degrees of freedom for the combined results.

2. Example SAS code for the by-subgroup analysis of the primary endpoint with imputation

Follow the same steps as for the example SAS code for the primary analysis except in the step 2 additional interaction terms need to be added.

Subgroup variable: Baseline HbA1c <8% or >=8%

```
ods output SLICES=SLICELSM1 SLICEDIFFS=SLICEDIFF1;
PROC MIXED DATA= EFFIM;
  BY imputation;
  CLASS USUBJID REGION WGTGR1 AGEGR1 PRIORDTX TRT01PN AVISITN HBGR1;
  MODEL CHG= HBGR1 REGION WGTGR1 AGEGR1 PRIORDTX TRT01PN AVISITN
TRT01PN*AVISITN HBGR1*TRT01PN HBGR1*AVISITN
          HBGR1*TRT01PN*AVISITN/ DDFM=KR;
  REPEATED AVISITN/SUB=USUBJID TYPE=UN;
  SLICE HBGR1*TRT01PN*AVISITN/sliceby(AVISITN='26') means pdiff cl
cov;
RUN;
```

Subgroup variable: Baseline Weight <90 or >=90 kg

```
ods output SLICES=SLICELSM2 SLICEDIFFS=SLICEDIFF2;
PROC MIXED DATA= EFFIM;
  BY imputation;

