11.12. Appendix 12: Sample Size Considerations

11.12.1. Sample Size Assumptions

[figure not shown]
[figure not shown]
This study will randomly assign approximately 150 subjects to each of the 2 treatment groups (liquid drug product and lyophilized drug product) in a 1:1 ratio, for a total of approximately 300 subjects. Eligible subjects will be stratified by age (<65 or ≥65 years of age), weight (<90 kg or ≥90 kg), and background antidiabetic therapy (diet and exercise or stable dose of metformin).

With 133 subjects in each of the 2 treatment groups, the study will provide 90% power to demonstrate non-inferiority for HbA1c change from baseline, assuming a non-inferiority margin of 0.4%, an expected treatment group difference of 0.0%, and a common standard deviation of 1%, using a 2-sample, 1-sided t test with significance level of 0.025. Power was calculated using PASS [Hintze, 2013]. Assuming that 13% of subjects will be withdrawn early or will be lost to follow-up; therefore, approximately 150 subjects will be randomized in each treatment group.

The non-inferiority margin of 0.40 was selected based on the expected effect of the albiglutide lyophilized drug product as active control. Results from two HARMONY Phase III studies (subset of GLP112756 and GLP112753) for the comparison of the control albiglutide lyophilized drug product versus placebo were used in selecting the non-inferiority margin. The two studies are similar to the current study in terms of the population and the design; subjects were either on diet and exercise or metformin background therapy and received 30 mg of albiglutide then up-titrated to 50 mg albiglutide. The 95% confidence interval from the 2 Harmony studies for HbA1c change from baseline at week 24 for albiglutide lyophilized drug product difference from placebo is (-1.04, -0.75). The conservative effect in terms of the difference from placebo for HbA1c change from baseline at Week 24 for albiglutide lyophilized drug product versus placebo is 0.75% (M1 =0.75%, as defined in Guidance for Industry: Non-Inferiority Clinical Trials [FDA, 2010]). M2, calculated as 50% of M1 is 0.375 (approximately 0.4). The margin of 0.40% that should be met in this trial will preserve at least 45% of the effect of the comparator and it is below M1.

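### The non-inferiority p-values promised for the nine tipping-point scenarios are specified without the 0.4 margin, so the recipe as written returns a test of zero difference

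*SAP*

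**What the plan says.** SAP 11.6.3.4 sets three monthly rates of HbA1c increase in each arm, giving nine combinations, and states: "The resulting treatment differences and associated P-values for non-inferiority will be tabulated against the varying rates". The display is Table 2.19. Protocol 9.4.5.4 makes the same promise without naming a procedure.

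The SAP then gives the recipe. Step 5 is to "save the difference in LSmeans between treatment group and the associated standard error from each of the 100 analyses". Step 6 pools these in PROC MIANALYZE: "The treatment differences, confidence intervals and p-values will be estimated by MODELEFFECTS and STDERR statement". The only further setting is: "Use the degrees of freedom (EDF) you would have if the dataset were complete". Neither step mentions 0.4, a null value or a one-sided test.

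For the primary analysis, Step 3 of SAP 7.1.1.1 uses the same pooling recipe. The only printed code that pools a treatment difference, in SAP 11.11.1, opens with "PROC MIANALYZE DATA=SLICEDIFF" and continues with MODELEFFECTS and STDERR alone. SAP 2.4 places the null hypothesis beyond a difference of 0.4%. SAP 2.4 and 7.1.1.1 conclude non-inferiority when the upper confidence limit is at or below 0.4%. No section defines a non-inferiority p-value.

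**The concern.** A non-inferiority p-value measures evidence against a difference beyond the margin, so the margin must enter the calculation. Here it does not. An estimate and its standard error, with no null value given, cannot produce a test against 0.4. The procedure falls back on its default null of zero and reports a two-sided p.

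The two tests answer different questions. The test of zero gives a large p when the arms agree, which is the result that supports non-inferiority. It gives a small p when they differ clearly in either direction. Table 2.19 is the plan's display of robustness to data missing not at random. A reader who takes its p-value column as labelled could see a robust result as failing, or a failed scenario as passing.

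**Working it through.** **Inputs.** From SAP 11.12.1: margin 0.4, expected difference 0.0, SD 1, power computed "using a 2-sample, 1-sided t test with significance level of 0.025", 133 per arm for 90% power, about 150 per arm randomized, 13% dropout. From SAP 11.6.3.4: rates of 0, 0.1 and 0.2 per month, with a month counted as 4 weeks.

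**The plan's own figure.** A noncentral t calculation gives power 0.9015 at 133 per arm and 0.8993 at 132, so the stated 133 for 90% is reproduced. Inflating, 133/0.87 = 152.9, against approximately 150 in the plan.

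**Formulas.** Let d be the pooled difference, liquid minus lyophilized.
- SE = √(2/150) = 0.1155, with 298 degrees of freedom
- Printed p as specified: 2·P(T > |d|/SE)
- Non-inferiority p: P(T < (d − 0.4)/SE)
- Upper 95% limit: d + 0.227

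This takes the complete-data SE and ignores between-imputation variance.

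**By pooled difference.** For d = 0.3, the printed test uses 0.3/0.1155 = 2.60 and the non-inferiority test uses (0.3 − 0.4)/0.1155 = −0.87.

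| d | Printed p | Non-inferiority p | Upper limit |
|---|---|---|---|
| 0 | 1.000 | 0.0003 | 0.227 |
| 0.1 | 0.387 | 0.0049 | 0.327 |
| 0.2 | 0.084 | 0.042 | 0.427 |
| 0.3 | 0.0098 | 0.194 | 0.527 |
| 0.4 | 0.0006 | 0.500 | 0.627 |

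With 133 per arm (SE 0.1226) the pattern is the same: d = 0 gives 1.000 against 0.0006, and d = 0.3 gives 0.015 against 0.208.

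**By scenario.** Let d0 be the difference when both rates are zero. Assume 13% missing at Week 26 in each arm and one common gap of τ weeks since the last observation. Then d = d0 + 0.13 × (liquid rate − lyophilized rate) × τ/4. The largest shift is 0.13 × 0.2 × 2.5 = 0.065 for τ = 10, and 0.13 × 0.2 × 6.25 = 0.1625 for τ = 25.

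| d0 | τ | Rates (liquid, lyophilized) | d | Printed p | Non-inferiority p | Upper limit |
|---|---|---|---|---|---|---|
| 0 | any | 0, 0 | 0 | 1.000 | 0.0003 | 0.227 |
| 0 | 10 | 0.2, 0 | 0.065 | 0.574 | 0.0020 | 0.292 |
| 0 | 25 | 0.2, 0 | 0.1625 | 0.160 | 0.0203 | 0.390 |
| 0 | 25 | 0, 0.2 | −0.1625 | 0.160 | <0.0001 | 0.065 |
| 0.2 | any | 0, 0 | 0.2 | 0.084 | 0.042 | 0.427 |
| 0.2 | 10 | 0.2, 0 | 0.265 | 0.022 | 0.122 | 0.492 |
| 0.2 | 25 | 0.2, 0 | 0.3625 | 0.0019 | 0.373 | 0.590 |
| 0.2 | 25 | 0, 0.2 | 0.0375 | 0.746 | 0.0009 | 0.265 |
| −0.1 | 10 | 0, 0 | −0.1 | 0.387 | <0.0001 | 0.127 |
| −0.1 | 10 | 0.2, 0 | −0.035 | 0.762 | 0.0001 | 0.192 |

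The non-inferiority p is below 0.025 exactly where the upper limit is below 0.4. The printed p does not follow that rule. From d0 = 0 and τ = 25 it is 0.160 whichever arm is made worse. From d0 = 0.2 and τ = 25 it is 0.0019 in a scenario that fails and 0.746 in one that passes.

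**The case against.** **The plan never states a zero null.** This is correct. The zero null follows from the inputs named and the software default, and no code is printed for Step 6. The printed primary code is visibly incomplete: the text of SAP 7.1.1.1 asks for EDF, yet the call that pools the difference omits it. A missing option there does not show intent, and a programmer who reads the label might supply the margin. But Step 6 is itself the specification, and it names the procedure, statements, input and degrees of freedom without the margin.

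**The planned case gives no false reassurance.** From d0 = 0 the worst corner is 0.1625, where the printed p is 0.160. No cell has a small p, and p near 1 beside a difference near 0 would look odd. That stands for d0 = 0, where the error is a false alarm. It does not stand in general. A start of 0.1375 has an upper limit of 0.1375 + 0.227 = 0.365 and passes, yet its 25-week corner is 0.1375 + 0.1625 = 0.3. That corner fails with a limit of 0.527 while printing 0.0098.

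**The differences are tabulated alongside, and Step 6 also produces confidence intervals.** This limits the harm, since a careful reader could judge each scenario from the interval. However, the sentence on tabulation does not call for the interval in the table.

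**Stronger readings that the documents do not support.** A reader might infer that the p-value always shrinks as the liquid arm worsens, so that the whole grid is inverted. From d0 = −0.1 and τ = 10 it rises, from 0.387 to 0.762. A reader might also infer that the primary p-value is wrong. SAP 7.1.1.1 and 7.1.2 never label that p-value as one for non-inferiority, and the results presentation in 7.1.2 lists only the difference and its interval.

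**Conclusion.** The concern holds in limited form. The p-values labelled as non-inferiority p-values for Table 2.19 would, under the recipe as written, be two-sided p-values against zero. Nothing elsewhere in the protocol or SAP corrects this. The error is large where it applies: 1.00 against 0.0003 at a difference of 0, and about 0.01 against 0.19 at a difference of 0.3. It can mislead in either direction.

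It is confined to one column of one sensitivity table. Every confidence interval is unaffected, and so is the primary conclusion, which does not use a p-value.

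The figures rest on SD 1, 150 per arm and no between-imputation variance. The scenario figures also assume equal 13% missingness and a common gap of 10 to 25 weeks. Other values would change the numbers but would not bring the margin into the test.

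**What to change.** In Step 6 of SAP 11.6.3.4, set the null at the margin (THETA0=0.4) and state that the saved difference is liquid minus lyophilized. Report the one-sided lower-tail p, P(T ≤ (estimate − 0.4)/SE), against 0.025. Print the upper limit of the 95% confidence interval for each scenario in Table 2.19, so that the p-value and the decision rule can be read together.

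If a p-value is reported with the primary difference, either use the same null or label it as a test of zero.

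The cost is one SAS option and one sentence. No data, model or sample size changes.
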